### 8.5. Period of Observation

All patients will be required to be continuously enrolled in the health plan for at least 24 months. Patients will have a variable length baseline period of at least 12 months. The 12 months prior to the index date will be used to assess the majority of pre-index characteristics. However, for select measures, eg, number of prior biologic therapies, and years since first RA diagnosis, the entire variable length baseline period will be utilized.

Measures utilizing the variable length baseline are noted. All baseline periods will be censored at January 1, 2012. The twelve months following the index date will be used to assess outcomes including treatment patterns, and health care costs, utilization and medication effectiveness.

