 Clinical Classification Software (CCS) for ICD-9-CM. Agency for Healthcare Research and Quality, Rockville, MD. <http://www.hcup-us.ahrq.gov/toolssoftware/ccs/ccs.jsp>

Measure 	Score
Age (continuous)	-0.066
Gender 0: male 1: female	-0.092
Inflammatory marker test ordered 0: no 1: yes	0.60
Rehabilitation visit 0: no 1: yes	0.69
Rheumatoid factor test 0: no 1: yes	2.1
Felty's syndrome 0: no 1: yes	2.3
Number of platelet counts ordered 0 = 0 visits 1 = 1 visit 2 = 2 visits 3 = 3 visits 4 = 4+ visits	0.42
Number of chemistry panels ordered 0 = 0 panels 1 = 1 panel 2 = 2 panels 3 = 3 panels 4 = 4 panels 5 = 5+ panels	-0.14
Rheumatologist visit count 1 = 0 visits 2 = 1-4 visits 3 = 5+ visits	0.52
Intercept	6.5

- **Pre-index medications**-The most common medications used during the 12-month pre- and post-index periods will be identified. The most common 25 medications received will be identified.
- **Opioid, non-steroidal anti-inflammatory drug (NSAID) use**-The use of weak and/or strong opioids and/or non-steroidal anti-inflammatory drug (NSAID) during the 12-month pre- and 12-month post-index periods will be identified. The number of pharmacy claims for opioids and/or NSAIDs and the number of days from the index date to the first opioid and/or NSAIDs claim will be identified.

---

 Number of platelet counts, chemistry panels, and rheumatologist visits are counted 1 per person per day.

- **Opioid, NSAID use while persistent.** In addition to opioid/NSAID use during the follow-up, use of opioids/NSAIDs while persistent and after persistence will be identified in the 12-month follow-up period.
- **Corticosteroid use.** The use of oral corticosteroids during the 12-month pre- and 12-month post-index periods will be identified. In addition, the total prednisone-equivalent dose of oral corticosteroids will be calculated.
- **Pre-index visit with a rheumatologist.** A 0/1 flag will be created to determine if the patient had an ambulatory visits (office visit or outpatient visit) in which the physician was a rheumatologist in the 90 days before or on the index date. A separate variable will be created identifying the number of visits with a rheumatologist during the entire 12-month baseline. A flag will also be created identifying the presence of a rheumatologist visit in the entire variable length baseline and the number of visits in the variable length baseline.

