### 8.6.3. Treatment Patterns

- **Non-persistence.** A 0/1 flag will be created to identify if the patient is not persistent with tofacitinib before the end of the 12 month follow-up period.

Non-persistence will be identified based on a gap in treatment with the index medication or switching to another biologic.

Among patients with 1 year of follow-up, persistence through the end of the 1 year follow-up will be identified. Persistence will be identified based on the day supply (or presumed day supply) and fill dates of claims for the index medication (see [Table 2](#) for a listing of presumed day supplies). Persistence with the index medication will be defined as not having a gap in therapy of at least 60 days between fills/infusions. For retail pharmacy (RX) claims the day supply will be utilized. For Healthcare Common Procedure Coding System (HCPCS) claims a presumed day supply derived from the product label will be utilized. A gap of at least 60 days between the run-out date (service date + day supply-1) and the next service date will be considered non-persistence. Patients with early refills will be allowed to accumulate a stockpile of the index medication of up to 14 days for later use.

- **Post persistence treatment patterns.** Patients who are not persistent for the entire follow-up period will be classified into the following mutually exclusive categories based on the first occurrence of non-persistence: switch immediately, discontinue then restart, discontinue then switch, discontinue and never switch or restart.
  - **Switch immediately.** Patients will be classified as switching immediately if they initiate a non-index biologic before a 60-day gap in treatment is observed for the index medication.
  - **Discontinue then restart.** Patients will be classified as discontinuing and then restarting if there is a gap in the index therapy of at least 60 days and the first medication observed after the gap is the index medication.
  - **Discontinue then switch.** Patients will be classified as discontinuing and then switching if there is a gap in the index therapy of at least 60 days and the first medication observed after the gap is a biologic (including Tofacitinib) different from index medication.

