### **8.10. Data Analysis**

#### **Primary Objective**

- **To compare treatment patterns including dosing, concomitant medication use, adherence, persistence and switching** among tofacitinib+MTX patients who discontinue MTX vs. persist with MTX or experience interrupted MTX.

For this objective, treatment patterns will be summarized across the cohorts of interest. Specific treatment patterns include non-persistence with the index medication, receipt of an opioid, receipt of an NSAID, adherence with the index medication, adherence with MTX.

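### Opioid and NSAID use during and after tofacitinib persistence is measured over patient-specific windows, with no allowance for time at risk

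*Combined protocol and SAP*

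**What the plan says.** Section 8.6.2 plans two kinds of opioid and NSAID measure.

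- **Fixed window.** Use is recorded "during the 12-month pre- and 12-month post-index periods will be identified. The number of pharmacy claims for opioids and/or NSAIDs" are counted as well. There is also a timing variable: "the number of days from the index date to the first opioid and/or NSAIDs claim will be identified".
- **Split window.** As a supplement, "use of opioids/NSAIDs while persistent and after persistence will be identified in the 12-month follow-up period". The text does not say whether this is a yes/no flag, a count or a rate, and it gives no denominator.

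Section 8.6.3 sets the boundary between the two split windows: "Non-persistence will be identified based on a gap in treatment with the index medication or switching to another biologic". The gap is at least 60 days, counted from the run-out date.

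Section 8.5 fixes the total: "The twelve months following the index date will be used to assess outcomes including treatment patterns", and "All patients will be required to be continuously enrolled in the health plan for at least 24 months".

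Under the primary objective, Section 8.10 states: "Specific treatment patterns include non-persistence with the index medication, receipt of an opioid, receipt of an NSAID". Section 8.10.1 then covers all pre- and post-index measures. It gives counts and percentages for categorical variables and means, medians and standard deviations for continuous ones, by cohort, with tests such as the t-test, Mann-Whitney or chi-square. Section 8.10.2 names only cost outcomes and medication effectiveness as possible adjusted outcomes.

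**The concern.** Follow-up is 12 months for everyone, so a patient with more persistent time has less post-persistence time. The chance of at least one claim in a window, and the expected number of claims, both rise with its length. A comparison of raw flags or counts between MTX cohorts therefore mixes two things: how often patients use analgesics, and how long they stayed on tofacitinib. The second is compared separately as a treatment pattern.

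Unequal windows are plausible. Section 8.3 assigns cohorts on MTX gaps alone and does not require continued tofacitinib, so a patient who stops both drugs enters a cohort defined by an MTX gap and has a short persistent window. A difference in persistence could then be reported a second time, as a difference in analgesic use.

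The post-persistence window has a further gap. Patients persistent for all 12 months have no time in it. The plan does not say whether they are left out or counted as non-users.

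**Working it through.** The documents give no claim rate, persistence time or cohort size, so there is no planned figure to reproduce. The figures below illustrate the mechanism under assumptions.

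**Assumptions (not from the documents).** A constant claim rate r per month, the same in both cohorts and both windows, so there is no true difference. Cohort A persists 10 months; cohort B persists 8 or 6. r runs from 0.02 to 0.20. For the test only, 200 patients per cohort.

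**From the documents.** Total follow-up is 12 months (Section 8.5), so post-persistence time is 12 minus persistent time.

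**Formulas.** P(any claim in t months) = 1 − exp(−r·t). Expected claims = r·t.

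**At r = 0.05, 10 v 8 months:**

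- Persistent window: 1 − exp(−0.50) = 39.3% v 1 − exp(−0.40) = 33.0%.
- Post-persistence window: 1 − exp(−0.10) = 9.5% v 1 − exp(−0.20) = 18.1%.
- Fixed 12 months: 1 − exp(−0.60) = 45.1% in both.
- Mean claims while persistent: 0.50 v 0.40, ratio 1.25. Divided by time: 0.50/10 = 0.40/8 = 0.05, ratio 1.00.

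**Range:**

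| r | Persistent, 10 v 8 | After, 10 v 8 | Persistent, 10 v 6 | After, 10 v 6 | Fixed 12 months, both |
|---|---|---|---|---|---|
| 0.02 | 18.1% v 14.8% | 3.9% v 7.7% | 18.1% v 11.3% | 3.9% v 11.3% | 21.3% |
| 0.05 | 39.3% v 33.0% | 9.5% v 18.1% | 39.3% v 25.9% | 9.5% v 25.9% | 45.1% |
| 0.10 | 63.2% v 55.1% | 18.1% v 33.0% | 63.2% v 45.1% | 18.1% v 45.1% | 69.9% |
| 0.20 | 86.5% v 79.8% | 33.0% v 55.1% | 86.5% v 69.9% | 33.0% v 69.9% | 90.9% |

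**Chance of a spurious p < 0.05 in the persistent window, 200 per cohort.** At r = 0.05 and 10 v 8 months the difference is 0.064 and its standard error is √(0.393·0.607/200 + 0.330·0.670/200) = 0.048. So z = 1.33, and Φ(1.33 − 1.96) is about 0.26. Over the range of r it is 14% to 43% for 10 v 8 months and 49% to 98% for 10 v 6.

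**The post-persistence denominator.** Suppose 70% of one cohort and 50% of the other persist for 12 months, and the rest stop uniformly between months 2 and 10, with r = 0.05. Among those who stop, the mean chance of a post-persistence claim is 1 − (exp(−0.10) − exp(−0.50))/(8 × 0.05) = 25.4% in both cohorts. With everyone in the denominator it becomes 0.30 × 25.4% = 7.6% v 0.50 × 25.4% = 12.7%. The gap comes only from counting patients who have no time in the window. The restriction suffices here because stopping times are alike in both cohorts; where they differ, a rate is still needed.

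**The case against.** The strongest reply is that this is a supplementary measure and an unaffected one is already planned. That stands. Use and claim counts over the fixed 12 months are specified, and continuous enrolment keeps that window equal for all patients. The primary objective lists only "receipt of an opioid, receipt of an NSAID" and does not mention the split windows, which appear under clinical characteristics. A reader might infer that the primary comparison of opioid and NSAID use is biased. The documents do not support that, since receipt over the fixed 12 months is free of this problem.

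A reader might also infer that the plan prescribes an unadjusted flag tested by chi-square. It does not. The verb used is only that use will be identified, and the list of tests in Section 8.10.1 is given as examples. But that section covers all post-index measures, and neither it nor Section 8.6.2 supplies person-time, an offset or censoring. Followed as written, it leads to an unadjusted comparison, and a count would be distorted as well as a flag.

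The days-to-first-claim variable does not fill the gap. It runs from the index date, is not tied to either window, and has no rule for patients without a claim.

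Finally, every rate and duration above is assumed. If persistence is the same in the MTX cohorts, this bias between cohorts disappears.

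**Conclusion.** The point holds for the two split measures only. Their windows vary by patient and the plan makes no allowance for time at risk. If persistence differs between cohorts, the longer-persisting cohort will appear to use more while persistent and less afterwards. It would be wrong to conclude that it appears to use more throughout, because the sign reverses in the second window.

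With no true difference and 0.02 to 0.20 claims per month, the spurious gap while persistent is 3.3 to 8.1 percentage points for 10 v 8 months and 6.8 to 18.1 for 10 v 6. Afterwards it is 3.8 to 22.1 and 7.4 to 36.9 points in the other direction. These sizes rest on a constant, equal claim rate and on assumed persistence times. That persistence does differ is not established; it is one of the questions the study asks. The consequence is limited because the fixed 12-month measures are sound, but the split results could be misread and are easily put right.

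**What to change.** 1. Report each split measure as claims per 30 days at risk in its own window, using a Poisson or negative binomial model with a log person-time offset and robust or overdispersed errors.
2. Restrict the post-persistence measure to patients who became non-persistent, and report how many they are in each cohort.
3. State that the main between-cohort comparison of opioid and NSAID use is the fixed 12-month measure.
4. Define the date on which the persistent window closes. Section 8.6.3 defines a 0/1 non-persistence flag but no date; one can be derived from the fill and run-out dates already used.
5. If a time-to-event analysis of opioid or NSAID use, censored at the end of persistence, is also shown, state that the censoring may be informative.

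The cost is a short specification and extra code, with no new data. The small drawback is that the rates remain descriptive: stopping tofacitinib may itself be related to analgesic need, and a person-time denominator does not remove that.

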### 8.2.1. Inclusion Criteria

This study will include individuals who are privately insured and with Medicare Supplemental insurance paid for by their employers and initiating tofacitinib in combination with MTX for RA between 01 January 2014 and 31 January 2017. To be included in the final study sample, patients must meet the following inclusion criteria:

1. At least one claim for tofacitinib between 01 January 2014 and 31 January 2017 (the identification period).

- a. **Medication index date.** The index date will be the date of the first claim for tofacitinib during the identification period.

*Note: Patients will have a variable length baseline of at least a year long. The baseline period will be censored at January 1, 2012 based on licensed data availability. The majority of baseline measures will use data from the 12 months immediately prior to the index date. Select measures will use data during the entire variable length baseline.*

- b. Tofacitinib initiation. Patients must have a 2nd claim for tofacitinib within 60 days of the end of the days supplied from their index claim (at least two claims with no 60 day gap).
- c. Oral MTX initiation. Patients must have an initial prescription for oral MTX in the period between 30 days prior to index date and 30 days following index date followed by a 2nd prescription for oral MTX within 60 days of the end of the days supplied from their initial MTX claim (at least two claims/administrations with no 60 day gap).

2. Presence of The International Classification of Diseases, 9th Revision, Clinical Modification (ICD-9 CM) code for RA (in any position) during the one-year pre-index period or on the index date. ICD-9 = 714.0x-714.4x & 714.81 or ICD10 = M05.\* & M06.0\*-M06.3\* or M06.8\*-M06.9\*.

3. At least 18 years old as of the index date.

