- **Disease duration.** The number of days from the earliest claim with a diagnosis of RA in the variable length baseline until the index date will be identified. Disease duration will only be created during the variable length baseline.
- **Pre-index Out-of-pocket expenses.** The patient's total all-cause and RA-related out of pocket healthcare cost for healthcare services in the one year before the index date and during the entire variable length baseline period will be calculated.
- **Comorbidities of interest.** 0/1 flags will be created to identify the presence of the following comorbidities during the 12-month baseline period.
  - Cardiovascular diseases;
  - Chronic obstructive pulmonary disease (COPD);
  - Asthma;
  - Kidney disease;
  - Diabetes;
  - Depression;
  - Anxiety;
  - Liver disease;
  - Sleep disorders;
  - Hypertension;
  - Hyperlipidemia.

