- **Compare all-cause and RA-related health care utilization among tofacitinb+MTX patients who discontinue MTX vs. persist with MTX or experience interrupted MTX.**

For this objective descriptive analysis will be conducted. Utilization measures (flags and 12-month counts) will be presented per patient during the baseline and follow-up periods. In addition, for counts the change from baseline to follow-up will be calculated.

- **Compare all-cause healthcare costs among tofacitinib+MTX patients who discontinue MTX vs. persist with MTX or experience interrupted MTX.**

For this objective descriptive and multivariable analysis will be conducted. For the descriptive analysis, 12-month cost measures will be presented per patient during the baseline and follow-up. The change in 12-month costs from the baseline to the follow-up will also be calculated. In addition, total all-cause cost will be presented in each of the months of the baseline and follow-up. The mean cost in each month will be included on a figure demonstrating the trend in costs over time. Multivariable analysis of follow-up health care cost will also be conducted using generalized linear models (see [Section 8.10.3](#)).

- **Evaluate the primary and secondary objectives in cohorts of interest.**

All objectives will be evaluated for Commercial and Medicare Supplemental lives separately as well as by Monotherapy vs. Combination regimens as identified in [Section 8.10.2](#) and by prior biologic experience (0, 1, 2, 3+ at any time prior to index).

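### Disease duration and the any-time prior-biologic strata use an unequal look-back of about 1 to 5.1 years, so they partly reflect enrolment length and index date

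*Combined protocol and SAP*

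**What the plan says.** Section 8.2.1 sets the range of index dates: "At least one claim for tofacitinib between 01 January 2014 and 31 January 2017 (the identification period"). The same section fixes the earliest visible date: "The baseline period will be censored at January 1, 2012 based on licensed data availability". Section 8.5 adds the lower limit: "Patients will have a variable length baseline period of at least 12 months". The enrolment rule is a minimum only: "All patients will be required to be continuously enrolled in the health plan for at least 24 months". Nothing equalises history beyond it.

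Most baseline measures use the 12 months before index. Selected ones use all available history:

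- **Disease duration** (8.6.2) is the "number of days from the earliest claim with a diagnosis of RA in the variable length baseline until the index date". The section adds that it is created on the variable-length baseline only.
- **Prior-biologic strata** (8.4) are 0, 1, 2 and 3+ over all prior history. Section 8.10 evaluates every objective "by prior biologic experience (0, 1, 2, 3+ at any time prior to index"), whereas 8.4 speaks of selected outcomes.
- **Out-of-pocket cost** (8.6.2) is totalled "in the one year before the index date and during the entire variable length baseline period will be calculated".
- **Rheumatologist visits** and **biologic counts** (8.6.2) are likewise produced on both the 12-month and the variable-length window.

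No section lists look-back length as a variable, divides a total by it, or treats duration as capped by it. The Limitations (8.12.1) describe a 12-month baseline and do not mention the variable one.

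**The concern.** A count or an elapsed time taken over an unequal window grows with the window. A patient with long-standing RA who joined the plan a year before index cannot show much more than a year of disease. The same patient, enrolled since January 2012 and indexed in January 2017, can show about five. Likewise, the stratum with no prior biologics mixes patients observed for one year with patients observed for five.

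These variables matter to the analysis. Secondary objective 1 compares clinical characteristics between cohorts. The prior-biologic strata are a planned breakdown of the objectives. The variables in 8.6.2 are candidates for the multivariable models (8.10.2). Adjusting for a duration that partly records enrolment length removes less confounding by true disease duration than the label suggests. The decomposition in 8.10.6 would inherit the same weakness if duration is among the characteristics used.

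**Working it through.** The plan states no look-back range to reproduce, so the range is derived from its dates.

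**Inputs from the documents.** Earliest visible date 1 January 2012; index dates 1 January 2014 to 31 January 2017; minimum look-back 12 months.

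**Formula.** Maximum look-back = index date − 1 January 2012.

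| Index date | Maximum look-back | Years (days / 365.25) |
|---|---|---|
| 1 Jan 2014 | 731 days | 2.00 |
| 1 Jan 2015 | 1,096 days | 3.00 |
| 1 Jan 2016 | 1,461 days | 4.00 |
| 31 Jan 2017 | 1,857 days | 5.08 |

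The ceiling rises 1,857 / 731 = 2.5-fold with index date alone. Against the 12-month minimum, the widest contrast is 1,857 / 365 = 5.1-fold.

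**Raw totals.** At an assumed constant 4 rheumatologist visits a year, the variable-length count reads 4 × 1 = 4 at the minimum and 4 × 5.08 = 20.3 at the maximum. The per-year rate is 4 in both cases. Constant out-of-pocket spending scales in the same way.

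**Prior-biologic strata (illustration, rates assumed).** If new biologics start at a constant rate r per year, the chance of observing none over look-back L is exp(−rL).

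| r per year | L = 1 | L = 2 | L = 5.08 |
|---|---|---|---|
| 0.1 | 90% | 82% | 60% |
| 0.2 | 82% | 67% | 36% |
| 0.5 | 61% | 37% | 8% |

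Patients with the same underlying rate fall into the zero stratum at very different frequencies, depending only on how long they were observed.

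**Disease duration (illustration, distributions assumed).** Measured duration = min(true duration, look-back). Index date is uniform over the identification period. True duration is exponential with a mean of 3 to 10 years. Pre-index enrolment is 1 year plus an exponential with a mean of 2 to 8 years, and look-back is the smaller of enrolment and the ceiling above.

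| Mean true duration | Mean extra enrolment | Share capped by window | Correlation with look-back | Correlation with true duration |
|---|---|---|---|---|
| 3 y | 8 y | 37% | 0.30 | 0.69 |
| 5 y | 4 y | 58% | 0.50 | 0.49 |
| 10 y | 2 y | 79% | 0.73 | 0.26 |

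The first and last rows are the extremes of the twelve scenarios run. When disease is mostly recent and enrolment long, the variable mainly tracks disease. When disease is long-standing and enrolment short, it mainly tracks the window.

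**The case against.** Several points on the other side stand.

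- A reader might infer that all these measures are unstandardised. The documents do not support that. Out-of-pocket cost, rheumatologist visits and biologic counts also have 12-month versions, and most baseline measures use only the 12 months. For cost and visits, the defect is confined to the variable-length versions.
- A reader might infer that the methotrexate cohort comparison is biased. The cohorts are defined by gaps after index, and the documents give no reason why look-back or index date should differ between them.
- It is tempting to say that the strata should be rebuilt on 12 months. That equalises observation but misses more past users: at the assumed rate of 0.2 a year, 82% would be classed as having no prior biologic. The Limitations already warn that such patients may simply have been off therapy. Using all available history is a legitimate choice.
- Index month and year will be described (8.6.1, 8.10.1) and are candidate covariates, and 8.10.2 leaves room for further variables. This could absorb the index-date part of the variation. It cannot absorb differences in enrolment length, and nothing commits the models to include it.
- The 5.1-fold contrast compares extremes. The typical contrast is unknown.

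What remains is that disease duration has no fixed-window alternative, the any-time strata depend on look-back, and look-back itself is neither reported nor adjusted for.

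**Conclusion.** The point holds with limited scope. Followed as written, the rules give patients with the same history different disease durations and different prior-biologic strata, over a look-back of 1 to about 5.1 years. The same is true of the variable-length out-of-pocket totals and visit counts.

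The range follows from the plan's own dates. The illustrative percentages and correlations rest on assumed rates and distributions and show only the mechanism. The bias in any cohort comparison cannot be sized, because the documents give no distribution of look-back by cohort. If look-back is balanced across cohorts, the cost is misclassification and weaker confounder control rather than a systematic difference between cohorts.

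**What to change.** - Tabulate look-back length by cohort alongside the baseline characteristics.
- Express variable-baseline out-of-pocket cost and visit counts per year of look-back, or compare cohorts on the 12-month versions.
- Treat disease duration as observed time since first RA claim. Flag patients whose first RA claim falls near the start of their look-back as having at least that duration, with the margin for near set in advance. Scaling per year cannot repair this variable.
- Include look-back length in any model that uses duration or the any-time biologic count.
- Keep the any-time prior-biologic strata as planned, and repeat the stratified analyses with the 12-month count from 8.6.2 as a sensitivity analysis.
- Amend the Limitations so that they describe the variable baseline as well as the 12-month one.

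The cost is a little extra programming, some relabelling and one more model term. No new data are needed.
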